7.4 Data Sources

The main source of clinical and patient data will be the patients' medical record. Baseline characteristics (outlined in Section 7.3) will be extracted by the investigator from the medical records to the extent possible and recorded in the study CRFs. Data reported on the index date or subsequent follow-up visits will be captured by the site in CRFs.

Patients will be enrolled in the study at the location where they receive medical care for VHL. Baseline medical information and history will be abstracted at study entry and followup data collection will be conducted every 6 months throughout the study period. Data will be recorded in the EDC system by personnel at each study site using standardized approaches. All variables will be collected, as available, from the patient's medical records. As this is a non-interventional study, there are no mandatory requirements or collection timepoints for variables. The collected data will be available in the medical records as part of normal clinical practices, and all patient visits will be conducted according to the treatment physician's normal clinical practice. Thus, this study does not include mandatory visits, tests, or assessments, if data are not available in the patient's medical records, it will not be solicited. At the time of study start at each site, study personnel will provide general training on the expectations for data entry and sites are provided in the data entry guidance which will be used to guide medical chart abstractions and CRF completion.

	26
PRODUCT: MK-6482	PROTOCOL/AMENDMENT VERSION NO.: 6482-026/3.0
REVOPS ID NO: NIS102327	CORE DRC APPROVAL DATE: 28-NOV-2023
EPIDEMIOLOGY NO. (PE STUDIES ONLY): EP05047.006	CRC PRC APPROVAL DATE: N/A

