hemangioblastoma that require treatment per investigator's judgment for the primary effectiveness analysis. Minimal attrition is expected during the duration of the study as most patients will likely remain under the care of the treating physician, as observed for patients in the MK-6482-004 clinical trial (~90% of participants still on study with a median duration of \sim 3 years) given that these sites provide specialized care for patients with VHL disease. Enrollment will be closely monitored during the enrollment period and enrollment of patients with each VHL disease-associated tumor type (RCC, CNS hemangioblastoma) will be stopped once the target sample size for that tumor type is reached with overall recruitment into the registry stopped once the sample size requirement for both tumor types is met. As one patient can have both RCC and CNS hemangioblastoma requiring treatment, each would contribute to the required sample size for that tumor type. If this were to occur, it would result in less than 80 patients included in the effectiveness analysis. All eligible patients receiving belzutifan treatment (including those patients with VHL disease-associated pNET) will be included in the safety analysis.

Effectiveness analyses will be restricted to patients with VHL disease-associated RCC and/or VHL disease-associated CNS hemangioblastoma given these are the most common clinical manifestations and are associated with the greatest morbidity and mortality. All patients enrolled in the registry will be included in the safety analysis.

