7.4.1 Study Procedures

Study procedures to be performed at each visit are provided in Table 1.

Data collection	Index date ^a /enrollment visit	Routine follow-up visits ^b during the treatment
Informed consent	X ^c	
Inclusion/exclusion criteria	Х	
Demographics	Х	
Behavioral risk factors (alcohol, smoking)	Х	
Medical history and comorbidities	Х	
Concomitant medications	Х	Х
Disease/tumor characteristics	Х	Х
Prior anticancer treatment(s) (medications and procedures)	Х	
Belzutifan treatment administration	X ^a	Х
Hemoglobin	Х	Х
Oxygen saturation by pulse oximetry	Х	Х
Blood pressure	Х	Х
Estimated glomerula filtration rate (RCC patients only)	Х	
Serious adverse events	Х	Х
Subsequent anticancer treatment(s) (medications or procedures)		Х
End of observation/patient status (e.g., death, loss to follow-up, withdrawal of consent)		Х

Table 1Data Collection Timing

IEC=independent ethics committee; IRB=institutional review board; RCC=renal cell carcinoma

- ^a Date of first administration of belzutifan will be defined as the index date for the patient. The index date is the baseline date for data collection during belzutifan treatment exposure for patients who consent to participate in the study. Signed informed consent must be obtained prior to or within 30 days after the first initiation of belzutifan.
- ^b Clinic visits and data collected will be per the local standard of care, and is not dictated per protocol (only secondary data that was collected as part of usual care, for a purpose other than the study, will be used). The investigator will not be requested to undertake any assessment that they would not carry out in their normal practice.

PRODUCT: MK-6482	PROTOCOL/AMENDMENT VERSION NO.: 6482-026/3.0
REVOPS ID NO: NIS102327	CORE DRC APPROVAL DATE: 28-NOV-2023
EPIDEMIOLOGY NO. (PE STUDIES ONLY): EP05047.006	CRC PRC APPROVAL DATE: N/A

^c Age (in years) and sex for patients who were approached but who do not consent to participate in the study and reason(s) for not participating may be collected if agreed by IRBs/IECs.

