7.5 Study Size

The study is descriptive, and there is no hypothesis testing. Up to 100 patients with VHL disease-associated RCC, CNS hemangioblastoma or pNET will be enrolled in the registry.

The target sample size for the primary effectiveness analysis includes approximately 40 eligible patients with VHL disease-associated RCC and approximately 40 patients with VHL disease-associated CNS hemangioblastoma requiring treatment. Enrollment will be closely monitored during the enrollment period and enrollment of patients with each VHL disease-associated tumor type (RCC and CNS hemangioblastoma) will be stopped once the target sample size for that tumor type is reached with overall recruitment into the registry stopped once the sample size requirement for both tumor types is met. Given the frequency of tumor reductive procedures in MK-6482-004 (8% of RCC patients and 6% of CNS hemangioblastoma patients, with surgery or locally directed therapy during a median follow-up of \sim 3 years)⁴, this target sample size provides greater than 90% probability of observing at least one RCC procedure or one CNS procedure during follow-up.

A target sample of 40 RCC patients in the registry, offers reasonable statistical precision for estimating the true population estimate with an upper limit of the 95% confidence bound below the point estimate of 29% of patients in a separate VHL disease-associated RCC natural history study⁵ having at least one tumor reductive procedure within 2 years of follow-up (Table 2). There is limited published data on the natural history of patients with VHL disease-associated CNS hemangioblastoma.

⁴ based on 01-Apr-2022 cutoff (preliminary analysis)

⁵ unpublished data from MSD study (EP05047.00)

PRODUCT: MK-6482	PROTOCOL/AMENDMENT VERSION NO.: 6482-026/3.0
REVOPS ID NO: NIS102327	CORE DRC APPROVAL DATE: 28-NOV-2023
EPIDEMIOLOGY NO. (PE STUDIES ONLY): EP05047.006	CRC PRC APPROVAL DATE: N/A

Table 295% CI for the Cumulative Incidence of Health Outcome of Interest (Exact
Confidence Interval; Clopper-Pearson Method; PASS 2021)

Assumed incidence for RCC surgery and/or locally directed therapy	40 patients	
	LL	UL
4%	0.3%	15.5%
6%	1.0%	18.3%
8%	1.8%	21.1%
10%	2.8%	23.7%

CI=confidence interval, LL=lower limit, UL=upper limit, PASS=Power Analysis & Sample Size, RCC=renal cell carcinoma

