For observational studies, it is accepted that data could be missing or incomplete per the physician records. Incomplete and missing electronic CRF data will be flagged and collected as part of ongoing data quality monitoring in the study. Where information is not available, trained personnel or the study coordinator who are completing the electronic CRFs will be able to click a checkbox which records these data as 'Not Available'. Clicking this checkbox will lock all related fields in the form, thus reducing the probability of missing queries. Incomplete and missing electronic CRF data not related to critical data items will be flagged as non-critical or queried as 'Not Available' or 'Unknown' in the electronic CRF.

PRODUCT: MK-6482	PROTOCOL/AMENDMENT VERSION NO.: 6482-026/3.0
REVOPS ID NO: NIS102327	CORE DRC APPROVAL DATE: 28-NOV-2023
EPIDEMIOLOGY NO. (PE STUDIES ONLY): EP05047.006	CRC PRC APPROVAL DATE: N/A

Patient-level data for all patients enrolled in the study will be provided proactively by participating sites and will be anonymized. During the study, the MAH or designee may make site visits to review protocol compliance, compare electronic CRFs and individual patient's medical records to ensure that the study is being conducted according to pertinent regulatory requirements. Checking of the electronic CRFs for completeness and clarity, and cross-checking with source documents, may be required to monitor the progress of the study. Moreover, regulatory authorities of certain countries, IRBs/ IECs, and/or the Sponsor's Clinical Quality Assurance Group may wish to carry out source data checks and/or on-site audit inspections. Direct access to source data will be required for these inspections and audits; they will be carried out given due consideration to data protection and medical confidentiality.

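### The no-solicitation rule in Section 7.4 makes no exception for the primary outcome, so a procedure missing from the reviewed record is likely to be read as no procedure

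*Protocol*

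**What the plan says.** The primary outcome is the proportion of patients with at least one renal (RCC cohort) or CNS (hemangioblastoma cohort) tumor reductive surgery or locally directed therapy (Protocol Sections 6.1, 7.3.2 and 7.7.4).

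- **Source.** Section 7.4 calls the medical record the main source, takes all variables from it as available, sets no mandatory requirements for any variable, and adds that "if data are not available in the patient's medical records, it will not be solicited". Footnote b of Table 1 (Section 7.4.1) says that "only secondary data that was collected as part of usual care, for a purpose other than the study, will be used". No second source for procedures is described.
- **Scope.** Section 7.3.2 asks for all VHL-related procedures during follow-up, with no limit to those done at the enrolling site.
- **Unavailable items.** Section 7.6 gives the abstractor a Not Available box: "Clicking this checkbox will lock all related fields in the form, thus reducing the probability of missing queries". Section 7.7.1 bases percentages on non-missing observations.
- **Sites and rhythm.** Patients are enrolled where they receive VHL care. Section 7.1 expects little attrition, "given that these sites provide specialized care for patients with VHL disease". Follow-up is abstracted every 6 months (Sections 7.4 and 7.6).
- **Declared limitation.** Table 3 (Section 7.9) names misclassification from unverified records. The mitigation is to collect as much detail as each record holds.

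**The concern.** For a laboratory value, the rule in Section 7.4 is harmless: a missing hemoglobin shows as a gap. The primary outcome is different. It is a yes/no event, and an undocumented procedure looks the same as one that did not happen. It also spans urology, neurosurgery, ablation and radiation therapy, some of which may be delivered at another hospital.

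The Table 3 mitigation is circular here, because collecting everything in the record cannot find what is absent from it. If false-positive procedures are negligible, under-capture can only lower the proportion, which is the direction that flatters the product. Only two or three patients with an event are expected per cohort, so a single missed event is visible in the estimate. No later analysis can restore an outcome that was never collected.

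**Working it through.** **Inputs from Section 7.5**

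- n = 40 per cohort: "A target sample of 40 RCC patients in the registry, offers reasonable statistical precision", and likewise about 40 for CNS hemangioblastoma.
- Planning rates: "8% of RCC patients and 6% of CNS hemangioblastoma patients", over a median of about 3 years.
- Claim: "this target sample size provides greater than 90% probability of observing at least one RCC procedure or one CNS procedure during follow-up".
- RCC benchmark: the upper confidence limit is to lie "below the point estimate of 29% of patients in a separate VHL disease-associated RCC natural history study".

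**Assumed input:** m, the share of procedures missing from the reviewed record. The documents give no value; 10-30% is used for illustration.

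**Step 1. Reproduce the plan's figures.** Clopper-Pearson with x = 40p left unrounded gives 0.33-15.46% at 4%, 0.96-18.33% at 6%, 1.80-21.05% at 8% and 2.79-23.66% at 10%. All four rows of Table 2 are matched. The chance of at least one patient with a procedure is 1 - (1 - p)^40:

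- RCC: 1 - 0.92^40 = 96.4%
- CNS: 1 - 0.94^40 = 91.6%

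Each cohort is above 90%, as claimed.

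**Step 2. Apply under-capture.** Observed proportion = p(1 - m), assuming no false positives.

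| Cohort | m | Observed | Exact 95% CI | P(at least one) |
|---|---|---|---|---|
| RCC | 0 | 8.0% | 1.8-21.1% | 96.4% |
| RCC | 10% | 7.2% | 1.4-20.0% | 95.0% |
| RCC | 30% | 5.6% | 0.8-17.8% | 90.0% |
| CNS | 0 | 6.0% | 1.0-18.3% | 91.6% |
| CNS | 10% | 5.4% | 0.7-17.5% | 89.1% |
| CNS | 30% | 4.2% | 0.4-15.8% | 82.0% |

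The shift is 0.8 to 2.4 points for RCC and 0.6 to 1.8 points for CNS. The intervals without loss are 21.1 - 1.8 = 19.3 and 18.3 - 1.0 = 17.3 points wide.

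**Step 3. When does the CNS claim fail?** It holds at m = 5% (90.4%) and fails at m = 10% (89.1%). The crossing is where 1 - (1 - p)^40 = 0.90, so p = 1 - 0.1^(1/40) = 5.59%, and m = 1 - 5.59/6 = about 7%. This reads the claim cohort by cohort. If it means a procedure in either cohort, and the cohorts are treated as separate, the figure is 1 - 0.92^40 x 0.94^40 = 99.7%, and this degree of loss does not threaten it.

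**Step 4. One patient.** Expected patients with an event are 40 x 0.08 = 3.2 and 40 x 0.06 = 2.4. If one CNS patient's procedure is silently missed, the proportion is 1.4/40 = 3.5%. If that patient is instead marked Not Available and leaves the denominator under Section 7.7.1, it is 1.4/39 = 3.6%. Dropping a patient who had no procedure gives 2.4/39 = 6.2%. The box therefore does not repair a missed event.

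**Step 5. The RCC benchmark.** With an observed 8%, dividing the upper limit by the captured share gives 21.1/(1 - m). This reaches 29% at 1 - m = 21.1/29 = 0.73, that is, about 27% missed. For a true 29% to appear as 8%, capture would have to be 0.08/0.29 = 0.28, that is, about 72% missed.

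**The case against.** Several stronger readings are tempting, and the protocol does not support them.

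- **That only procedures done at the enrolling site count.** Section 7.4 speaks of the patient's medical records, and Section 7.3.2 asks for all VHL-related procedures. An outside craniotomy mentioned in a clinic letter or scan report is captured. What remains is the procedure that reaches no reviewed document.
- **That the protocol rules an undocumented procedure to be no procedure.** No such rule is written. Unavailable items are marked as such, and percentages use non-missing observations. The event-free reading is a practical consequence of an absence that nobody sees.
- **That sites are barred from obtaining outside reports.** The quoted clause ends a sentence explaining that a non-interventional study adds no visits, tests or assessments. An outside operative report is usual-care data. Still, nothing tells a site to look for it, and the wording discourages doing so.
- **That the bias is certain or large.** Patients are enrolled where they receive specialized VHL care and abstracted every 6 months. Tumor characteristics, serious adverse events and treatment interruptions are also collected and could reveal an operation. Section 7.6 provides checks on critical items and comparison with source records. These safeguards probably keep the loss low.
- **That the natural-history benchmark had better capture.** The protocol says only that its data came from routine surveillance at one institution. Completeness is not described, so a differential error cannot be claimed.

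It is also fair that CRF layout belongs to the data management plan and entry guidance, and that misclassification is declared. Neither settles the matter: Section 7.4 itself fixes a general rule with no exception for the primary outcome, and the declared mitigation does not reach undocumented events.

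**Conclusion.** The point holds as a modest, inexpensive improvement. Procedures absent from the reviewed record may be missed, the likely direction is a lower primary proportion, and Table 3 does not address it. At an assumed 10-30% missed, 8% reads as 7.2-5.6% and 6% as 5.4-4.2%. Taken by cohort, the probability of at least one CNS procedure falls below the stated 90% once about 7% are missed.

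This rests on an assumed miss rate, on negligible false positives and on the planning rates of Section 7.5. The shift is small beside sampling error. A reader might infer that the comparison with 29% is undone; at the planning rate of 8%, that would take about 27% missed even for the corrected upper limit to reach the benchmark. The reason to act is that the error runs in one direction and cannot be corrected after data collection.

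**What to change.** 1. In Section 7.4, exempt the primary outcome from the wording on no mandatory requirements and no solicitation.
2. At each existing 6-monthly entry, require a renal and a CNS procedure status: yes, no or unknown, covering other institutions, with the date of the last record that supports it.
3. Let sites, with the patient's consent, request outside operative or treatment reports. These are usual-care secondary data and fit footnote b of Table 1.
4. Do not let the Not Available box close this item.
5. Treat unknown as not observed after the last confirmed date, not as no procedure. Report the share of follow-up with confirmed status beside the primary proportion.
6. Extend the information-bias row of Table 3 to say how outside procedures are ascertained.

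**Cost:** some added data entry and record requests at the sites, and one line in the consent form. No visit, test or assessment is added. Questioning patients directly is optional: it would be primary data collection, and Section 9, which rests on secondary use of data, would have to be reviewed first.

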7.4.1 Study Procedures

Study procedures to be performed at each visit are provided in Table 1.

Data collection	Index date ^a /enrollment visit	Routine follow-up visits ^b during the treatment
Informed consent	X ^c	
Inclusion/exclusion criteria	Х	
Demographics	Х	
Behavioral risk factors (alcohol, smoking)	Х	
Medical history and comorbidities	Х	
Concomitant medications	Х	Х
Disease/tumor characteristics	Х	Х
Prior anticancer treatment(s) (medications and procedures)	Х	
Belzutifan treatment administration	X ^a	Х
Hemoglobin	Х	Х
Oxygen saturation by pulse oximetry	Х	Х
Blood pressure	Х	Х
Estimated glomerula filtration rate (RCC patients only)	Х	
Serious adverse events	Х	Х
Subsequent anticancer treatment(s) (medications or procedures)		Х
End of observation/patient status (e.g., death, loss to follow-up, withdrawal of consent)		Х

Table 1Data Collection Timing

IEC=independent ethics committee; IRB=institutional review board; RCC=renal cell carcinoma

- ^a Date of first administration of belzutifan will be defined as the index date for the patient. The index date is the baseline date for data collection during belzutifan treatment exposure for patients who consent to participate in the study. Signed informed consent must be obtained prior to or within 30 days after the first initiation of belzutifan.
- ^b Clinic visits and data collected will be per the local standard of care, and is not dictated per protocol (only secondary data that was collected as part of usual care, for a purpose other than the study, will be used). The investigator will not be requested to undertake any assessment that they would not carry out in their normal practice.

PRODUCT: MK-6482	PROTOCOL/AMENDMENT VERSION NO.: 6482-026/3.0
REVOPS ID NO: NIS102327	CORE DRC APPROVAL DATE: 28-NOV-2023
EPIDEMIOLOGY NO. (PE STUDIES ONLY): EP05047.006	CRC PRC APPROVAL DATE: N/A

^c Age (in years) and sex for patients who were approached but who do not consent to participate in the study and reason(s) for not participating may be collected if agreed by IRBs/IECs.

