6 RESEARCH QUESTIONS AND OBJECTIVES

The primary aim of this registry is to characterize the effectiveness of belzutifan for patients with VHL disease-associated RCC and/or CNS hemangioblastoma treated in real-world clinical practice. The primary effectiveness parameter includes tumor reductive procedures given the clinical importance of this parameter and association with subsequent morbidity and mortality of disease.

Secondary aims are to describe potential serious adverse events (SAEs), occurrence of new VHL disease-associated tumors or tumor type, and metastasis during belzutifan use and to evaluate treatment patterns among all new users of belzutifan.

6.1 **Primary Objective**

- 1. Among new users of belzutifan with VHL disease-associated RCC, to describe the proportion of patients who undergo at least one renal tumor reductive surgery (e.g., nephrectomy) or locally directed therapy (e.g., radiofrequency ablation).
- 2. Among new users of belzutifan with VHL disease-associated CNS hemangioblastoma, to describe the proportion of patients who undergo at least one CNS tumor reductive surgery (e.g., craniectomy) or locally directed therapy (e.g., radiation therapy).

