Patients will be followed from enrollment and treatment until the end of observation, defined as the earliest of withdrawal of consent, loss to follow-up, death, or until the end of the study. The planned minimum follow-up for each patient will be 3 years, noting that with a median duration of treatment follow-up of 2.4 years in the pivotal trial (MK-6482-004)², the majority of surgeries and reports of disease progression occurred within ~3 years of treatment, and the highest exposure-adjusted event rate occurred within 3 months of treatment. The non-interventional study duration considers the feasibility of running a long-term prospective observational cohort study while maintaining scientifically robust assessments. With a planned enrollment of patients within 2-3 years, the planned maximum follow-up for patients in the registry will be up to 5-6 years.

Up to 100 patients with VHL disease-associated RCC, CNS hemangioblastoma or pNET will be enrolled in the registry. This includes approximately 40 patients with VHL disease-associated RCC and approximately 40 patients with VHL disease-associated CNS

² 15-Jul-2021 database lock

	2
PRODUCT: MK-6482	PROTOCOL/AMENDMENT VERSION NO.: 6482-026/3.0
REVOPS ID NO: NIS102327	CORE DRC APPROVAL DATE: 28-NOV-2023
EPIDEMIOLOGY NO. (PE STUDIES ONLY): EP05047.006	CRC PRC APPROVAL DATE: N/A

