7.3.1 Exposure

Treatment initiation and subsequent dose modification will be at the discretion of the treating physician. Exposure will be documented from the date the patient received a first dose of belzutifan (index date).

Primary exposure definition: Patients included in this registry will be considered exposed to belzutifan if they receive at least one dose. Participants will be followed until the end of observation, defined as the earliest of withdrawal of consent, loss to follow-up, death, or until the end of the study.

For the analysis of safety, patients will be considered as treated for up to 90 days after discontinuation of therapy or 30 days after a treatment switch.

Data captured on belzutifan treatment exposure, e.g.,:

- Start date, starting dose, duration of therapy
- As applicable, treatment interruption, reason for interruption, and date that drug was resumed
- As applicable, treatment discontinuation and reason for discontinuation
- As applicable, dose reduction and reason for dose reduction

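### Table 1 limits follow-up data collection to the treatment period, contradicting the sections that follow patients and collect procedures to end of observation; applied literally, it would bias the primary proportion low

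*Protocol*

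**What the plan says.** **Table 1 (Section 7.4.1).** Section 7.3 sends the reader to Section 7.4.1 for collection timing, and that section points to Table 1. The table has two columns: index date or enrollment, and routine follow-up visits "during the treatment". There is no column for time after discontinuation. The row that captures the primary outcome, "Subsequent anticancer treatment(s) (medications or procedures"), is marked only in the second column, and so is "End of observation/patient status (e.g., death, loss to follow-up, withdrawal of consent"). SAEs and tumor characteristics are marked in both columns, so after the index date they too depend on the treatment column. Footnote a states: "The index date is the baseline date for data collection during belzutifan treatment exposure".

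**The rest of the protocol.**
- Section 7.1: "Patients will be followed from enrollment and treatment until the end of observation". The end points listed are withdrawal of consent, loss to follow-up, death and study end. Stopping belzutifan is not one of them. Section 7.3.1 repeats this.
- Section 7.3.2 collects all VHL-associated procedures over follow-up, with no treatment limit.
- Sections 7.4 and 7.6 plan abstraction every 6 months for the whole study period.
- Sections 7.3.1 and 7.7.6, for safety: "patients will be considered as treated for up to 90 days after discontinuation of therapy", or 30 days after a switch.

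**Secondary outcomes.** The Section 6 aims refer to "metastasis during belzutifan use and to evaluate treatment patterns among all new users of belzutifan". The study information table and the abstract use a similar limit. The formal objectives in Section 6.2 do not, and Section 7.3.2 speaks of follow-up.

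**The concern.** Table 1 is the protocol's statement of when each item is collected, and nothing says that it yields to the text where the two differ. A site or CRF builder who takes it at its word would close procedure capture when belzutifan stops.

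The primary analysis (Sections 7.7.1 and 7.7.4) is a crude proportion with an exact interval. A patient whose first procedure comes after discontinuation would be counted as having had none, yet would remain in the effectiveness population, which requires only one dose. The error runs in one direction. It also bears on the planned benchmarking against natural-history data, where under-capture makes belzutifan look better. Patients who stop because of insufficient benefit are plausibly among those closest to a procedure: Section 5 describes the eligible population as one in which an intervention may be inevitable. SAEs in the post-discontinuation part of the safety window would be exposed to the same loss.

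**Working it through.** **1. Inputs (Section 7.5).** Target n = 40 per tumor type. Assumed procedure proportions are 8% (RCC) and 6% (CNS) over a median follow-up of about 3 years. The protocol claims a greater than 90% probability of at least one procedure. The RCC benchmark is 29% within 2 years. No discontinuation rate is given anywhere.

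**2. The plan's own figures.** P(at least one) = 1 − (1 − p)^40.
- RCC: 1 − 0.92^40 = 96.4%.
- CNS: 1 − 0.94^40 = 91.6%.

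Both exceed 90%. Clopper-Pearson limits with n = 40 and x = 40p give 0.3–15.5%, 1.0–18.3%, 1.8–21.1% and 2.8–23.7%, matching Table 2. No sample-size figure is wrong on this point.

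**3. Effect of under-capture.** Let s be the share of patients with a procedure whose first one falls after discontinuation and is not recorded. Recorded proportion = p × (1 − s). The values of s are assumptions.

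| s | RCC recorded (true 8%) | RCC upper 95% limit | CNS recorded (true 6%) | P(at least one CNS) |
|---|---|---|---|---|
| 0 | 8.0% | 21.1% | 6.0% | 91.6% |
| 10% | 7.2% | 20.0% | 5.4% | 89.1% |
| 25% | 6.0% | 18.3% | 4.5% | 84.1% |
| 50% | 4.0% | 15.5% | 3.0% | 70.4% |

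At s = 25%: 0.08 × 0.75 = 0.060; 0.06 × 0.75 = 0.045; 1 − 0.955^40 = 84.1%.

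The last column reads the greater-than-90% claim as applying to each tumor type. If it means either type, and the two groups are treated as independent, the figure is 1 − 0.92^40 × 0.94^40 = 99.7%. It becomes 1 − 0.94^40 × 0.955^40 = 98.7% at s = 25%, still above 90%.

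**4. What s might be if the procedure hazard does not change off drug.** Take h = −ln(0.92)/3, and d = −ln(1 − D)/3 for an assumed proportion D discontinuing by 3 years. The on-treatment incidence is h/(h + d) × [1 − 0.92 × (1 − D)].
- D = 10%: 7.6% of the total 8.0% is captured, so 5% is missed.
- D = 50%: 5.8% of 8.0% is captured, so 28% is missed.

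**5. Scale.** Expected patients with a procedure are 40 × 0.08 = 3.2 (RCC) and 40 × 0.06 = 2.4 (CNS). At s = 25% the expected loss is 0.8 and 0.6 of a patient.

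**The case against.** The strongest reply is that the text already requires full collection. Five sections point to end of observation, against one column header and one footnote clause. Table 1 itself suggests loose wording: its treatment column holds end-of-observation status, which need not occur on treatment. Footnote a defines a baseline date and sets no explicit end to collection. Section 7.4 says that data entry guidance will steer chart abstraction, and that guidance is not shown. This stands, and it makes the bias conditional. It does not remove the contradiction, which Table 1 states in two places.

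A reader might infer more than the documents support:
- *That the protocol defines the primary outcome in two ways.* It does not. Sections 6.1, 7.3.2 and 7.7.4 put no on-treatment limit on procedures. The limit to belzutifan use concerns secondary outcomes only.
- *That this is informative censoring.* Nobody is censored in a crude proportion. The problem would be under-ascertainment.
- *That the safety window cannot be filled.* That follows only if collection really stops with treatment.
- *That up to two thirds of procedures would be missed.* Giving every discontinuer the 29%-in-2-years rate, with D from 10% to 50%, puts the missed share at 22% to 67%. But D is invented, and an untreated rate is applied to everyone who stops, for any reason. The 8% is not stated to be on-treatment only, so events may be counted twice. Section 7.5 gives no such benchmark for CNS.

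The loss at modest s is also small beside the sampling error: the Table 2 interval at 8% is 21.1 − 1.8 = 19.3 points wide, and its upper limit is below 29% with or without the loss. That tempers the urgency. A one-directional error that wording can remove is still worth removing.

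**Conclusion.** The contradiction is real and concerns capture of the primary outcome. If Table 1 is applied literally, the primary proportion can only be biased low, provided that a patient without a recorded procedure is counted as having had none. The size cannot be derived from the documents. The 25% case (8% recorded as 6.0%, 6% as 4.5%, and the CNS probability of at least one procedure 84.1% instead of 91.6%) is an illustration, not an estimate. It falls below the stated 90% only when that claim is read per tumor type. The intended design is evidently follow-up to end of observation, so this is a should-fix inconsistency and not a flaw in the design. The differing windows for metastasis and new tumors are a separate, secondary wording point.

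**What to change.** 1. Re-head the Table 1 follow-up column as 6-monthly abstraction from index date to end of observation, on or off belzutifan, and correct footnote a to match. Confirm that SAE collection covers at least the safety window already defined in Section 7.3.1.
2. State in Section 7.3.2 that procedures count through end of observation regardless of treatment status.
3. Separately, reconcile the window for metastasis and new tumors in Section 6, the study information table and the abstract with Section 7.3.2.
4. Check that the CRF and data entry guidance follow the corrected table.

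A supportive on-treatment analysis is optional and can be left to the SAP.

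The cost is protocol and guidance wording. Six-monthly abstraction throughout the study is already planned and uses records of usual care, so no visit, test or assessment is added and the sample size is unchanged.
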